### 7.3.B. ADDITIONAL ANALYSES

The sample will be characterized using descriptive methods (Demographic and Medical History Questionnaire, PPECS) and standard/raw scores (SSP, Vineland-3, M-ABC-2). Feasibility and acceptability of the intervention will be determined by participants' daily duration of singlet wear and qualitative responses to the semi-structured interview conducted post-intervention.

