#### *6.6.D. CRITERIA FOR DISCONTINUATION/MODIFICATION*

Withdrawal of informed consent is possible at any time, without any obligation for the child or caregiver to give reasons for the decision. Tolerance, compliance, and adverse events will be monitored during each weekly assessment visit or by telephone call from a member of the research team. Should any serious adverse events or other concerns about wellbeing occur, the child will discontinue the intervention and return to standard care. In these such cases, the child will be invited to remain in the study and attend the remaining assessment visits.

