#### *6.6.E. STRATEGIES TO IMPROVE/MONITOR ADHERENCE*

After the researcher has supplied child participants their singlet and supported their first wear, they will provide the caregiver with strategies to support and encourage their child's singlet wearing and manage challenging behaviour should it arise. A researcher will telephone the caregiver at least three times during the intervention phase – once each during each of the acclimatization and full-scale wearing weeks – to check how the child is doing and troubleshoot any issues arising. During the intervention phase, the length of time the child spends wearing the singlet will be reported each day by the caregiver via a smartphone-based experience sampling app.

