### 6.7.C. OTHER OUTCOMES

Other outcomes of this trial include:

- Intervention feasibility and acceptability indicated through duration of daily singlet wear – as captured through experience sampling – and semi-structured interviews conducted with children and their caregiver(s) in weeks 0 and 5. This will provide valuable first-hand insights into the feasibility and acceptability of JettProof sensory singlets.
- Caregiver effort expended to support their child as measured by the Parent Effort Scale (PES; Pfeiffer et al., 2017) in weeks 1 and 5. The PES has shown adequate internal consistency and test-retest reliability in an autistic sample (Bevans, Hallock, Piller, & Pfeiffer, 2022).
- Caregiver stress as measured by the Parent Stress Index-4th Edition Short Form (PSI-4-SF; Abiden, 2012) in weeks 1 and 5. The PSI-4-SF has shown good internal consistency and test-retest reliability in a variety of samples (Abiden, 2012).

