#### *6.8.C. ASSESSMENT SCHEDULE*

Child participants will attend six face-to-face assessment visits (See Figure 1 & Table 1) with their caregiver(s) during each of the trial weeks. Assessment visits at weeks 1 through 5 will each involve a researcher fitting the child with an Empatica E4 wristband on the wrist or calf. Empatica E4 recordings will be taken while children watch a low-demand movie (Inscapes) to ascertain their physiological baseline, and while completing Lab-TAB (H. Goldsmith et al., 2010) episodes interspersed with a period

of free-play with their caregiver. Additional assessments conducted at weeks 1 and 5 include the M-ABC-2 and COMPS-2, and at week 5 an examiner-led interview to explore child and caregiver perceptions and experiences of the singlet. All assessment sessions will be video-recorded with consent from caregivers for later scoring.

The caregiver will be given a laptop during each of their child's assessment visits and navigated to a REDCap survey to complete: GAS (Kiresuk & Lund, 1994) in weeks 1 through 5, in addition to the SCAS-P (Nauta et al., 2004), PES (Pfeiffer et al., 2017). Additionally, the PSI-4-SF (Abiden, 2012) will be completed via hardcopy in weeks 1 and 5. Caregivers who do not manage to complete all survey measures during their child's assessment visit will be provided a survey return code, enabling them to return to the survey for later completion (within 24 hours). The PSI-4-SF may be taken home for completion and return at the child's next assessment visit. Assessment visits in Weeks 2, 3 and 4 will require a time commitment of around one hour for children and their caregiver(s). A longer time commitment of two hours will be required for visits in Weeks 1 and 5.

During the trial period, the caregiver will receive a push notification on their smartphone from their installed MyCap application three times per day (morning, afternoon, evening) to report their child's previous night's sleep (morning, only), current activity, affect, use of non-routine medications (evening, only), and singlet wearing (intervention phases, only). The resulting daily time commitment for caregivers will be approximately 6 minutes (2 minutes per day).

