### 7.3.C. HANDLING OF MISSING DATA

The last observation carried forward (LOCF) method (i.e., replacing each missing score with the last observed score preceding the missing score) will be used where for experience sampling ratings provided multiple times within a phase, and for measures administered multiple times across subphases within a phase (i.e., from pre-intervention/baseline to post-intervention/return to baseline, from acclimatization to full-scale intervention phases). Listwise deletion will be used in other cases of missing data.

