### 7.5. ADVERSE EVENTS AND SAFETY

The deep-touch compressive pressure produced by the singlet might cause minor physical discomfort and/or secondary physical sensations (e.g., itching, tingling) arising from the activation of sensory nerve endings in the skin. Qualitative work we have performed in preparation for this study – i.e., focus group discussions with clinicians who prescribe JettProof garments, thematic analysis of customer testimonials posted to the JettProof website – suggests that discomfort is experienced for a small proportion of wearers and is likely to resolve over time as acclimatization occurs. For this reason, children's first wear of the singlet will be supervised by a trained occupational therapist and a one-week acclimatization period will allow gradual increased exposure to the singlet before proceeding to full-scale wearing (i.e.,  $\geq 6$  hours per day). A researcher will telephone each caregiver at least once per week during the intervention phase (i.e., three times in total) to monitor for the occurrence of any adverse events associated with the singlet.

Our qualitative work has indicated that caregiver attempts to doff JettProof garments (e.g., for laundering) may be met with child refusal, upset (e.g., crying) and other challenging behaviour (e.g., tantrum). As such, each family will be provided three singlets for the intervention phase, allowing

substitution while laundering. Further – in an effort to make trial events more predictable for child participants and ensure ample time for them to prepare for transitions across trial phases – each child will be given a printed visual schedule at the beginning of the trial to take home with them, that illustrates the sequence of study activities and singlet wearing. This schedule will be reviewed at each study visit with the child and with the caregiver by phone as needed by the trained occupational therapist research assistant. Lastly, a researcher will telephone each caregiver during their child’s post-intervention/return to baseline phase to monitor for the occurrence of adverse events associated with *removal* of the singlet.

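### The missing-data rule in Protocol 7.3.C does not exempt singlet wear time, so a child who stops wearing the singlet and whose app entries cease is credited with the last reported hours instead of 0 h

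*Protocol*

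**What the plan says.** Protocol 7.3.B says that feasibility and acceptability will be determined by participants' "daily duration of singlet wear and qualitative responses to the semi-structured interview conducted post-intervention". Wear time is the only quantitative input of the two.

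Three sections make wear time an experience sampling variable. Section 6.6.E states that "the length of time the child spends wearing the singlet will be reported each day by the caregiver" through the smartphone app. Section 6.7.C describes daily wear "as captured through experience sampling". Section 6.8.C lists singlet wearing among the app items for the intervention phases.

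Section 7.3.C then sets the missing-data rule. LOCF "will be used where for experience sampling ratings provided multiple times within a phase", and also for measures repeated across subphases, including from acclimatization to full-scale wear. For everything else, "Listwise deletion will be used in other cases of missing data". No sentence treats wear time differently or gives a value for days after the singlet has been abandoned.

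**The concern.** A missing affect or sleep rating is unknown, and LOCF is a guess at it. Wear after a child has given up the singlet is not unknown: it is 0 h. Carrying forward the last positive report therefore turns evidence against acceptability into evidence of adherence.

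Stopping is foreseen. Section 6.8.B leaves wearing time to the child's comfort, 6.6.D has children come off the singlet if there are serious adverse events or other wellbeing concerns and invites them to stay in the study, and 7.1.B keeps protocol deviators in the trial. Section 6.3 expects most children to reach at least 6 h/day in the full-scale phase, and the feasibility results are meant to inform a larger trial. With 10 children, each one misclassified shifts the proportion by a tenth.

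**Working it through.** The protocol gives no computed figure on this point, so there is none to reproduce. The check has two parts: what the rule does, and how large the effect can be.

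**What the rule does to a silent stop**

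- LOCF: every later day takes the last reported hours.
- Listwise deletion by child: the child leaves the summary, which raises it whenever that child's true wear is below the average of the others.
- Listwise deletion by day: only the days before the stop remain, so the child's mean is the pre-stop level.
- None of these gives 0 h for the days after the stop.

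**Inputs**

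- From the protocol: full-scale phase of two weeks = 14 days (6.4); 10 children (6.9); 6 h/day (6.3).
- Assumed: hours per day before the stop (*h*), last full-scale day worn (*d*), and no app entries afterwards.

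**One child.** True mean = *h* × *d* / 14. LOCF mean = [*h* × *d* + *h* × (14 − *d*)] / 14 = *h*.

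| *h* (h/day) | *d* | True mean | LOCF mean | Days ≥ 6 h, true | Days ≥ 6 h, LOCF |
|---|---|---|---|---|---|
| 6 | 3 | 18/14 = 1.29 | 6.0 | 3 of 14 | 14 of 14 |
| 6 | 7 | 42/14 = 3.00 | 6.0 | 7 of 14 | 14 of 14 |
| 6 | 10 | 60/14 = 4.29 | 6.0 | 10 of 14 | 14 of 14 |
| 8 | 3 | 24/14 = 1.71 | 8.0 | 3 of 14 | 14 of 14 |
| 8 | 7 | 56/14 = 4.00 | 8.0 | 7 of 14 | 14 of 14 |
| 8 | 10 | 80/14 = 5.71 | 8.0 | 10 of 14 | 14 of 14 |

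If the child stops at the end of acclimatization with a last report of 6 h, and that value is carried into the full-scale phase, the true mean is 0 and the LOCF mean is 6.0.

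If wear tapers first (3 days at 8 h, 2 days at 2 h, then silence), the true mean is (24 + 4)/14 = 2.0 and the LOCF mean is (24 + 4 + 9 × 2)/14 = 3.3. The child is below 6 h either way.

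**Group of 10.** Seven children at 8 h, two at 4 h, one silent stop with *h* = 8 and *d* = 3:

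| | Mean (h/day) | Reaching 6 h |
|---|---|---|
| True | (56 + 8 + 1.71)/10 = 6.57 | 7/10 = 70% |
| LOCF | (56 + 8 + 8)/10 = 7.20 | 8/10 = 80% |
| Listwise, child dropped | (56 + 8)/9 = 7.11 | 7/9 = 78% |

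Each such stop adds (8 − 1.71)/10 = 0.63 h/day to the group mean under LOCF. If all other children wear 8 h, then 1, 2 or 3 silent stops give true means of 7.37, 6.74 or 6.11 h/day, against 8.0 under LOCF or with those children dropped.

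**When the statement about most children changes.** Take 'most' as more than half. Let *r* be the number truly reaching 6 h and *k* the number of silent stops whose last report was at least 6 h.

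- LOCF changes the statement if *r* ≤ 5 and *r* + *k* ≥ 6: *k* = 1 with *r* = 5; *k* = 2 with *r* = 4 or 5; *k* = 3 with *r* = 3, 4 or 5.
- Dropping the child changes it if *r* ≤ 5 and *r*/(10 − *k*) > 0.5: *k* = 1 with *r* = 5 (5/9); *k* = 2 with *r* = 5 (5/8); *k* = 3 with *r* = 4 or 5 (4/7, 5/7).

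For example, if eight children start at 6 h or more and three of them stop silently, LOCF reports 8/10 and the truth is 5/10.

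**The case against.** The strongest reply is that the error needs a chain of events: the child stops, the last report is above zero, and every later prompt goes unanswered. Section 6.8.C sends three prompts a day and does not confine the wear item to one of them, so a single answer after the stop would probably record no wear, and LOCF would then carry 0. Staff would also find out: under 6.6.D, "Tolerance, compliance, and adverse events will be monitored during each weekly assessment visit" or by telephone, and under 7.5, "A researcher will telephone each caregiver at least once per week during the intervention phase". A stop they know of is arguably not a missing value at all. 'Ratings' fits affect better than hours worn, and the unit of listwise deletion is not defined. Wear is a descriptive outcome read alongside interviews, 6 h/day is not a formal decision rule, and scoring details of this kind are often left to an SAP.

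Much of this stands as a limit on frequency and size. There is no error when the caregiver goes on entering 0 h, and little when hours taper. The 7/9 and 7.1 h figures do depend on dropping the whole child.

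It does not remove the defect. Experience sampling is the named source for wear, and nothing written lets what staff learn at a visit or call override the fill-in rule. Deleting days instead of children still leaves the example child at 24/3 = 8.0 h/day. The interviews are qualitative and do not correct the wear figure. An SAP could add an exemption, but none was available, and the protocol itself already states a rule that is wrong for this variable.

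**Conclusion.** The concern holds. Followed as written, 7.3.C replaces a true 0 h with the last positive report for a child who stops and goes silent, and the alternative reading also flatters the result in the typical early-stop case.

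For an individual child the error can be large: 1.7 against 8.0 h/day in the example. For the group it is about 0.6 h/day and one child in ten for each such stop. Whether most children are said to reach 6 h changes only when the true count is close to half; in the main worked group it does not change.

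These sizes rest on assumed hours, stop days and complete silence afterwards. The protocol gives no basis for estimating how often that will happen. The point should be corrected, but it does not threaten the trial as a whole.

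**What to change.** In 7.3.C:

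- Exempt singlet wear time from LOCF.
- Score every day after a known stop or withdrawal from wearing as 0 h, taking the stop date from the planned weekly visits and calls.
- Leave unexplained gaps from children who are still wearing the singlet as missing, and report how many days they cover.

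In 7.3.B, report the proportion reaching 6 h/day out of all enrolled children, and list each stop with its day and any reason given. The listing is reporting detail; the change to 7.3.C is the essential part.

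The cost is two or three sentences and no new data collection, because the contacts that supply the stop date are already scheduled. The wear figures may come out lower.

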### 7.3.C. HANDLING OF MISSING DATA

The last observation carried forward (LOCF) method (i.e., replacing each missing score with the last observed score preceding the missing score) will be used where for experience sampling ratings provided multiple times within a phase, and for measures administered multiple times across subphases within a phase (i.e., from pre-intervention/baseline to post-intervention/return to baseline, from acclimatization to full-scale intervention phases). Listwise deletion will be used in other cases of missing data.

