## 6.9. SAMPLE SIZE

In this feasibility study, we will recruit 10 participants in order to provide initial insights into the intervention feasibility and protocol as well as preliminary effect size estimates in the context of pragmatic constraints (i.e., time, budget).

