## 7.3. STATISTICAL METHODS

### 7.3.A. OUTCOME ANALYSES

This single-case feasibility study will combine visual and quantitative analyses of the data. For each participant, scores for each repeated outcome measure (i.e., Empatica E4 recordings, Lab-Tab, GAS, PES-H, PES-C, PSI-4-SF) will be graphically depicted as a time-series with standard deviation bands around each series and the global average for each outcome measure plotted as a reference line. Visual analysis will be employed for an initial examination of within-subject slope and level change across trial phases. Effect sizes will be computed through parametric methods (i.e., standard mean difference [Hedges *g*]) and non-overlap indices (e.g., Tau-U), with a *p*-value of < .05 indicative of statistical significance.

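### Listwise deletion of what LOCF cannot fill can discard a child's observed weeks in a series of 10, although the planned per-child analyses need no complete record

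*Protocol*

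**What the plan says.** Section 7.3.C of the protocol has two rules, applied in order.

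- LOCF comes first. It is used "for experience sampling ratings provided multiple times within a phase" and "for measures administered multiple times across subphases within a phase". The second group is explained as running "from pre-intervention/baseline to post-intervention/return to baseline, from acclimatization to full-scale intervention phases". As written, a week 1 score may therefore fill week 5, and a week 2 score may fill weeks 3 and 4.
- Everything else falls under the second rule: "Listwise deletion will be used in other cases of missing data". The section does not say whether the unit deleted is the child from every analysis, the child for that outcome, or the single record.

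Three other places bear on this. Section 7.3.A analyses the data child by child and outcome by outcome: "For each participant, scores for each repeated outcome measure" are graphed, and effect sizes are computed as Hedges g and non-overlap indices such as Tau-U. Section 6.9 sets the size of the series: "we will recruit 10 participants in order to provide initial insights into the intervention feasibility and protocol". Section 6.6.D shows that observations are wanted even after the singlet is stopped, since "the child will be invited to remain in the study and attend the remaining assessment visits".

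**The concern.** In its usual sense, listwise deletion drops the case, not the missing value. That suits methods that need a complete row for each subject. The methods in section 7.3.A do not: a child with weeks 1, 3, 4 and 5 observed can still be graphed and still gives a comparison between phases. If week 2 is missing, LOCF has no earlier score within the intervention phase to carry, so deletion applies and the four observed weeks could be lost.

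With 10 children, each one lost matters. Section 6.10 selects the sample on purpose to span a range of sensory difficulties, so losing one child may remove a profile. The loss may also be selective. Section 7.5 has a Lab-TAB task stopped at once if the child reacts more than mildly or shows challenging behaviour, and section 6.7.A takes the primary E4 signals during those tasks. Children who are more dysregulated are therefore plausible candidates for incomplete records.

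**Working it through.** The protocol derives N = 10 from pragmatic limits and gives no missing rate, so there is no figure of its own to reproduce. The check asks how many of 10 children would be kept under each reading.

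**Inputs**

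- From section 7.1.A, Table 1: three measures at weeks 1 to 5 (E4, Lab-TAB, GAS) and five at weeks 1 and 5 (M-ABC-2, COMPS-2, SCAS-P, PES, PSI-4-SF). That is 3×5 + 5×2 = 25 values per child. E4 is counted once because its four signals come from one device. PES is counted once. Experience sampling is left out because LOCF covers it.
- Assumed: each value is missing independently with probability m = 5% or 10%.

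**Values that LOCF cannot fill (k)**

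- LOCF as written (week 1 to week 5; week 2 to weeks 3 and 4): weeks 1 and 2 of a five-visit measure and week 1 of a two-visit measure. Across all outcomes k = 3×2 + 5×1 = 11.
- LOCF only within weeks 2 to 4: weeks 1, 2 and 5 of a five-visit measure and both visits of a two-visit measure. Across all outcomes k = 3×3 + 5×2 = 19.

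**Children kept by deletion: 10×(1−m)^k**

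| Reading | k | m = 5% | m = 10% |
|---|---|---|---|
| Per outcome, five-visit, LOCF as written | 2 | 9.0 | 8.1 |
| Per outcome, five-visit, LOCF within weeks 2–4 | 3 | 8.6 | 7.3 |
| Per outcome, two-visit, LOCF as written | 1 | 9.5 | 9.0 |
| Per outcome, two-visit, week 5 not filled | 2 | 9.0 | 8.1 |
| Across all outcomes, LOCF as written | 11 | 5.7 | 3.1 |
| Across all outcomes, LOCF within weeks 2–4 | 19 | 3.8 | 1.4 |

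**Children kept using all observed values**

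- Five-visit measure, needing at least one of weeks 2 to 4 and at least one of weeks 1 and 5: 10×(1−m³)×(1−m²) = 9.97 at 5% and 9.89 at 10%.
- Five-visit measure, if week 1 itself is required: 10×(1−m³)×(1−m) = 9.5 and 9.0. The gain over deletion with LOCF as written is then about 0.5 and 0.9 of a child.
- Two-visit measure: both visits are needed, so 10×(1−m)² = 9.0 and 8.1. This equals per-outcome deletion with week 5 not filled, so nothing is gained. The higher 9.5 and 9.0 under LOCF as written include children whose week 5 score is a copy of week 1.

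**Sensitivity**

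- Sections 6.8.C and 7.1.A put GAS at weeks 1 to 5, but section 6.7.A puts it at weeks 1 and 5. If GAS is a two-visit measure, k across outcomes is 2×2 + 6 = 10 or 2×3 + 6×2 = 18. The numbers kept become 6.0 and 3.5, or 4.0 and 1.5.
- Independence makes deletion across outcomes look worse than it would be if whole visits are missed. If all measures at a visit are missing together and nothing else is, a child is lost for a missed week 1 or 2 (or 1, 2 or 5). The across-outcome figures then equal the per-outcome five-visit ones: 9.0 and 8.1, or 8.6 and 7.3.

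**The case against.** The strongest reply is that LOCF is applied first, so deletion is only a residual rule, and that an analysis run separately for each child and outcome gives a missing motor score no route to remove that child's GAS series. A team following section 7.3.A might well drop only the single record. The exact unit could also be set in a statistical analysis plan that is not at hand. Much of this stands: deletion across all outcomes is one reading, not the evident intent. But the protocol fixes the method by name, and that name usually means dropping the case.

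Several stronger conclusions are tempting and are not supported.

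- A reader might infer that any missed visit costs the whole series, which at 10% missing would leave 0.90^5 = 59% of children. That ignores LOCF; with it the figure is 73% to 81%.
- A reader might treat the four E4 signals as independent chances of loss. They come from one wristband and would often be lost together.
- A reader might infer that feasibility is overstated. Section 7.3.B judges feasibility by daily wear time and interviews. Wear time comes from experience sampling, which LOCF covers, so this deletion does not touch it.
- A reader might infer that benefit is overstated. Selective loss is plausible from the stopping of Lab-TAB tasks, but nothing in the protocol establishes its direction or size.
- A reader might see section 6.6.D as contradicted. It is not: visits attended after stopping the singlet yield data, and deletion does not target those children. They are exposed only if an earlier value is missing.

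**Conclusion.** The concern holds in a limited form. For values that LOCF cannot fill, section 7.3.C names a method that can discard observed weeks, and the planned analyses gain nothing from it. On a five-visit measure, per-outcome deletion costs about 1 to 1.4 of 10 children at 5% missing and 2 to 3 at 10%, where using all observed values costs almost none. The benefit shrinks if week 1 is treated as indispensable, and there is none for two-visit measures. Deletion across outcomes could remove more than half the series at 10%, but only on the strictest reading and with missing values scattered independently. If single-record deletion is what was meant, nothing beyond the missing value is lost and the amendment merely says so.

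All sizes rest on assumed missing rates. Using all observed values does not by itself remove bias if missingness depends on distress. The carrying of week 1 scores into week 5 is a separate question that this point does not settle.

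**What to change.** Replace the listwise sentence in section 7.3.C with:

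> A missing value removes only that observation for that outcome; each child stays in every analysis that their observed data support; the number of observed values and the reasons for missing values are reported per child, outcome and phase.

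This governs only values that the LOCF rule does not fill and leaves that rule as it stands. It needs no new data and no new method. A group mixed model is not required, and it would be a debatable addition to a design that section 6.2 chose in order to avoid group-level conclusions. The costs are small: children will contribute unequal numbers of observations, which the reported counts make visible, and a child missing week 1 or week 5 on a two-visit measure still has no pre-post contrast for it.
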